4.6.3. Subject Discontinuation and Termination	Subjects who wish to withdraw from the study should complete the procedures associated with the Week § 12/EOT visit at the nearest study visit and the Follow-up Week 12 16/EOS visit 4 weeks later.	The treatment period of the study was lengthened to 12 weeks. The follow-up visit is now on Week 16.
4.6.3. Subject Discontinuation and Termination	The term discontinuation generally refers to a permanent halt in study drug administration.  The reason for subject discontinuation or withdrawal from the study will be recorded on the electronic Case Report Form (eCRF). A complete comprehensive physical examination, body weight, vital	Subjects who discontinue study drug early will not be required to do procedures.

Section	Version 3	Rationale
	signs measurement, 12 lead ECG, laboratory analysis, urine pregnancy test for females of child-bearing potential, urine sample for urinalysis, and an assessment of concomitant medications and AEs will be performed at the closest study visit, according to Section 4.6.1.	
5.1.3. Demographics	5.1.3. Demographics  Demographic data including date of birth, age, sex, ethnicity, and race will be collected as indicated in Table 4.	A demographics section was added to align with the Schedule of Assessments.
5.1.4. Medical History	5.1.4. Demographic/Medical and Surgical History A complete medical history, including surgical history, alcohol, tobacco, and nicotine-containing product use histories for the past 5 years, will be taken at Screening for the last 5 years. All relevant	Demographics were moved to Section 5.1.3. to align with the Schedule of Assessments.
·	changes throughout the study after Screening will be recorded in the subject's source document and electronic case report form (eCRF) as AEs.	Only relevant changes from baseline will be recorded as AEs.
5.1.5. Prior and Current Concomitant Medications	Prior opioid use to manage DPNP will be recorded for the past 5 years prior to Screening.	Collecting additional details on history of opioid use.
5.1.5. Safety Assessments	5.1.5. Safety Assessments  Overall safety and tolerability will be assessed by the incidence of TEAEs and SAEs and by evaluations of change from baseline in physical examination, vital signs, 12 lead ECGs, and clinical chemistry, hematology, coagulation, and urinalysis lab tests.	This section was replaced with Section 5.1.6. Adverse Events.
5.1.6. Adverse Events	5.1.6. Adverse Events Investigators and study staff are responsible for detecting, documenting, and reporting AEs and SAEs. For each subject, reporting of AEs and SAEs begins after written informed consent/assent is provided. Throughout the study, subjects will be provided opportunities to report AEs. For more information on AEs, see Section 6.3.	This section is to replace Section 5.1.5. Safety Assessments to align with the Schedule of Assessments.
5.1.7. Electronic Diary Set-up	Subjects will also complete the DSIS via their e-diary daily upon waking, preferably in the morning.	Redundant text was removed.
5.2. Clinical Procedures/Assessments	5.2.1. Height and Weight Measurement Height will be measured only at Screening; the subject will not wear	Height and weight were separated into 2 sections to align with the

Section	Version 3	Rationale
	shoes during the measurement of height.  5.2.2. Weight Measurement  Body weight will be measured at the times indicated in Table 4.  Weight should be taken with no shoes, hats, and outerwear. Body mass index will be calculated at Screening for eligibility.	Schedule of Assessments.
5.2.3. Comprehensive Physical Examination	5.2.3. Comprehensive Physical Examination	Physical Examination was separated into 2 sections to align with the Schedule of Assessments.
5.2.4. Targeted Physical Examination	5.2.4. Targeted Physical Examination	Physical Examination was separated into 2 sections to align with the Schedule of Assessments.
5.2.5. Electrocardiogram	Baseline for clinical assessments will be those measurements obtained prior to study drug administration on Day 1. Another ECG will be performed approximately 1-hour postdose on Day 1.	An additional ECG at 1-hour postdose was added based upon recommendation from the FDA.
5.2.6. Vital Signs Measurements	The average of the second and third readings will be assessed and calculated as part of the submission data processing and assessed.	Additional detail was removed, as this will be covered in the SAP.
5.3. Laboratory Procedures/Assessments	Samples will be stored under conditions stipulated in the Central Laboratory Manual until they are transported for measurement.  Samples will be transported and measured by a central laboratory.	Additional guidance provided for the care of lab samples.
5.3.1. Pregnancy Tests for Females of Child-bearing Potential	5.3.1. Pregnancy Tests for Women-Females of Child-bearing Potential A serum and or urine pregnancy test will be performed at the times indicated in Table 4. A serum pregnancy test will be performed at Screening for women females of child-bearing potential (WOCBP) or at any point in time if a pregnancy is suspected.	The word "woman" was replaced by "female" throughout the protocol for consistency.
5.3.6. Clinical Chemistry	Samples will be collected for the following clinical chemistry analyses as indicated in Table 4: ferritin, creatine kinase, blood urea nitrogen, enzymatic creatinine, eGFR, total bilirubin, direct bilirubin, alanine aminotransferase (ALT), aspartate aminotransferase (, AST), alkaline phosphatase, amylase, lipase, sodium, potassium, calcium, phosphorus, uric acid, total protein, glucose, albumin, lactate dehydrogenase, magnesium, chloride,	Amylase and lipase will now be included in the clinical chemistries.

Section	Version 3	Rationale
	bicarbonate, and gamma glutamyl transferase.	
5.3.7. Hemoglobin A1c	5.3.7. Hemoglobin A1e Samples will be collected for HbA1c as indicated in Table 6. Detailed instructions on collection, storage, and shipment of the samples will be provided in the Central Laboratory Manual provided to the Investigator.	This text was moved to Section 5.3.11. of the protocol.
5.3.8. Fasting Lipid- Profile	5.3.8. Fasting Lipid Profile Samples will be collected for the following lipid assessments as indicated in Table 6: total cholesterol, low density lipoprotein (LDL), high density lipoprotein (HDL), and triglycerides.	This text was moved to Section 5.3.12. of the protocol.
5.3.11. Hemoglobin A1c	5.3.11. Hemoglobin A1c Samples will be collected for HbA1c as indicated in Table 4. Detailed instructions on collection, storage, and shipment of the samples will be provided in the Central Laboratory Manual provided to the Investigator.	This text was moved from Section 5.3.7. of the protocol.
5.3.12. Fasting Lipid Profile	5.3.12. Fasting Lipid Profile Samples will be collected for the following lipid assessments as indicated in Table 4: total cholesterol, low-density lipoprotein, high-density lipoprotein, and triglycerides. Subjects should fast for at least 8 hours prior to clinic visits where fasting lipids are taken (Screening, Week 4, Week 8, Week 12, and Week 16).	This text was moved from Section 5.3.8. of the protocol.  Additional guidance on fasting was provided,
5.4.1. Rescue Medication	5.4.1. Rescue Medication Allowed rescue medication includes NSAIDs or acetaminophen to be used as needed and not to exceed the maximum dose stipulated in this protocol (Section 7.8.3). Subjects will be instructed to take no more than 3000 mg per day of acetaminophen (eg, 500 mg every 4 to 6 hours and not exceeding the daily limit) or 1200 mg/day of ibuprofen (eg, 200-400 mg every 4 to 6 hours as needed and not exceeding the daily limit).	This text also included in Section 7.8.3. The duplicated text was removed.

Section	Version 3	Rationale
5.4.1. Pain Evaluation	Diabetic peripheral neuropathy (DPN) occurs in approximately Approximately 50% of subjects with diabetes experience DPN and at around 15- to 20% of subjects with diabetic neuropathy have pain in the feet. Alleviation of pain is the is a primary goal and cornerstone of subject management. Treatment is available and to date there are three The approved treatments for DPNP include 3 oral medications to treat DPNP (duloxetine, pregabalin, and tapentadol) and a topical patch (containing 8% capsaicin), though). Of these, tapentadol (an opioid medication) and the 8% capsaicin patches are prohibited per protocol, see Section 7.8.4. The approved medications are suboptimal and both effective pain relief and suboptimal effectiveness and tolerability remain elusive and is. Thus, a large unmet medical need remains for the treatment of DPNP.	This text was edited to clarify that although tapentadol and 8% capsaicin patches are approved to treat DPNP, they are prohibited per the protocol.
5.4.1.1. Numeric Pain Rating Scale	In order to highlight how people experience pain sensations differently and how the unpleasant aspects of pain can differ from pain intensity, subjects will report how they perceive their average pain intensity, worst pain intensity, and pain upon walking other characteristics of their pain during the past 24 hours at bedtime, using the 11-point NPRS as per Table 4.  The NPRS of pain intensity is a numeric scale, ranging from 0 (representing no pain at all) to 10 (representing the worst pain imaginable) (Figure 3). The subject selects a whole number (0 to 10) that best indicates the intensity of his/her pain in the past 24 hours. Subjects must have a score of at least ≥4 on the NPRS at Screening and an average NPRS pain intensity score of at least ≥4 during the last 7 days prior to randomization- with a minimum of 5 measurements (Section 4.2.1).  The results from this PRO will be used to determine the efficacy of RTA 901 in achieving at least a 30% and or a 50% decrease in pain scores after 8 12 weeks of treatment.	The description of the NPRS was edited for clarity.  The treatment period of the study was lengthened to 12 weeks.
5.4.1.2.Daily Sleep Interference Scale	The DSIS is will be completed daily by subjects upon waking (3-minute self-administered questionnaire), preferably in the morning, to accurately capture variability in sleep interference due to pain, thus minimizing recall bias.	Repeated text about DSIS was consolidated into this section.

Section	Version 3	Rationale
T.11 4 C.1 11 2	Wook &	
Table 4: Schedule of Assessments (Part 1 & 2)	Week 3       Week 4       Week 5       Week 6       Week 7       Week 8       Week 12       Week 12       Week 12       EOSd	The treatment period of the study was lengthened to 12 weeks. The

Section	Version 3	Rationale
	Day 22 Day 29 Day 36 Day 43 Day 50 Day 57 Day 71 Day 71 F5785 (±2) Day 85 113 (±2)	visits on Weeks 3, 5, and 7 were removed and additional visits were included on Weeks 10 and 16. The EOT visit will now by at Week 12 and the follow-up visit is now on Week 16.
Table 4: Schedule of Assessments (Part 1 & 2)	Adverse events were added to the Screening visit.	Adverse events were included in the Screening visit, as AEs are collected after the ICF is signed.
Table 4: Schedule of Assessments (Part 1 & 2)	c Day 1 includes the first dose administration, and all procedures must be performed before study drug administration, except for adverse events, 1-hour postdose ECG,	An additional ECG at 1-hour postdose was added based upon recommendation from the FDA.
Table 4: Schedule of Assessments (Part 1 & 2)	d Subjects who discontinue study drug early for any reason should complete the procedures associated with the Week \$12 /EOT visit at the nearest study visit and the Follow-up Week 1216 /EOS visit 4 weeks later.	The treatment period of the study was lengthened to 12 weeks. The follow-up visit is now on Week 16.
Table 4: Schedule of Assessments (Part 1 & 2)	g Height should be measured with no shoes.	The height should be measured without shoes.
Table 4: Schedule of Assessments (Part 1 & 2)	j ECG on Day 1 should be recorded at predose and 1-hour postdose.	An additional ECG at 1-hour postdose was added based upon recommendation from the FDA.
Table 4: Schedule of Assessments (Part 1 & 2)	n Subjects should fast for at least 8 hours prior to clinic visits where fasting lipids are taken (Screening, Week 4, Week 8, Week 12, and Week 16).	Additional guidance provided for fasting on days where fasting lipids are measured.
Table 4: Schedule of Assessments (Part 1 & 2)	o -All study drug administration should be performed in an early fasted state, defined as having no food within at least 2 hours prior to study drug administration and for 1 hour following study drug administration. Since the first dose will be taken in-clinic and there	Additional guidance for fasting prior to visits was provided.

Section	Version 3	Rationale
	are no fasting lipids taken at the Run-in visit, subjects should fast for 2 hours prior to the visit.	
Table 4: Schedule of Assessments (Part 1 & 2)	P On visits containing both labs with fasting and study drug administration, the longer of the fasting guidance (8 hours) is to be followed, these are not additive.	Additional guidance provided for managing fasting based on the visit.
Table 4: Schedule of Assessments (Part 1 & 2)	q Subjects will complete the NPRS in the e-diary daily at bedtime. r Subjects will complete the DSIS in the e-diary daily upon waking.	Additional guidance to denote the PROs performed daily on the e-diary.

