## 4.6. Study Drug Discontinuation, Interruption, and Subject Termination

## 4.6.1. Discontinuation of Study Drug

Discontinuation from study drug does not mean discontinuation from the study. Subjects who discontinue the study drug early for any reason should complete the procedures associated with the Week 12/EOT visit at the closest study visit. If the subject discontinued study drug during a study visit, the EOT procedures should be performed during that study visit. If the subject discontinues study drug in between visits, he/she will perform the EOT procedures at the next scheduled study visit. The subject will then complete the procedures associated with the Week 16/end of study (EOS) visit 4 weeks after discontinuation.

If a clinically significant (CS) finding is identified (including, but not limited to changes from baseline) after enrollment, the Investigator or qualified designee will determine if any change in subject management is needed. Any new clinically relevant finding will be reported as an AE.

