### 8.4.8. Analysis of Safety Variables

The number and percent of subjects with an AE will be summarized for each treatment group. Changes from baseline to each scheduled time point for physical examinations, vital sign measurements, ECGs, clinical laboratory measurements, and body weight will be summarized by treatment group.

In addition, the number and percent of subjects with a predefined abnormality in clinical laboratory tests will be summarized by treatment group.

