	doses of up to 160 mg and multiple daily doses (for 14 days) of up to	
	80 mg (Study 901-C-1503) using RTA 901	
	_	
	Additionally, at the highest proposed dose of 80 mg QD, there is at least a 40-fold safety margin based on the data from the 3-month	
	GLP toxicity studies in mice and monkeys (Table 8 of the IB).	
	Based on the clinical multiple dose study (901-C-1503),	
	These exposures are similar to or above the exposures at the	
	efficacious doses in the rodent models of diabetic neuropathy	
	In summary, at the proposed doses for Part 1, RTA 901 is predicted	
	to have efficacious and safe exposure in subjects with DPNP, with a	
	10 mg dose anticipated to be an efficacious dose and 80 mg the	
	highest feasible dose with potentially maximal efficacy and an	
	acceptable safety profile. However, based on the exposures	
	associated with efficacy in the nonclinical models, it is possible that a dose lower than 10 mg may need to be explored to identify the	
	minimally effective dose in subjects with DPNP and thereby enable a	
	robust phase 2 dose ranging study. Therefore, a planned interim E-R	
	analysis for efficacy from the first 96 subjects in Part 1 of this study	
	has been incorporated to recommend the optimal doses for	
	investigation in Part 2. Eligible doses for selection in Part 2 will be limited to a dose range of 1 to 80 mg. Part 2 doses will not exceed	
	80 mg, at which there is at least a 40-fold safety margin based on the	
	data from the 3-month GLP toxicity studies in mice and monkeys.	
	2.1.1. Primary Objectives	Subheadings were added to denote
2.1.1. Primary Objectives	2.1.1.1. Efficacy	the primary efficacy and safety
	• To assess the efficacy of RTA 901 based on change from baseline in	objectives of the study.

Section	Version 3	Rationale
	the average daily pain score using the Numeric Pain Rating Scale (NPRS) after 812 weeks of treatment 2.1.1.2. Safety  • To assess the safety and tolerability of RTA 901 during and following the Treatment Period	Additional detail was included on the method for determining the primary efficacy objective based upon recommendation from the FDA.
		The Treatment Period of the study was lengthened to 12 weeks.

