2.1. Study Objectives and Endpoints

Study Primary Objectives

Efficacy:

 To assess the efficacy of RTA 901 based on change from baseline in the average daily pain intensity score using the Numeric Pain Rating Scale (NPRS) after 12 weeks of treatment

Safety:

 To assess the safety and tolerability of RTA 901 during and following the Treatment Period

Study Primary Endpoints

Efficacy:

 Change from baseline in the average daily NPRS pain intensity score during Week 12

Safety

Frequency, intensity, and relationship to study drug of adverse events and serious
adverse events and change from baseline in the following assessment: physical
examinations, vital sign measurement, electrocardiograms, clinical laboratory
measurements, and body weight.

[figure not shown]
Study Secondary Objectives

 To assess the efficacy of RTA 901 in achieving at least 30% decrease in the NPRS pain intensity score after 12 weeks of treatment

- To assess the efficacy of RTA 901 in achieving at least 50% decrease in the NPRS pain intensity score after 12 weeks of treatment
- To assess the percentage of subjects using rescue medication for diabetic peripheral neuropathic pain (DPNP) treatment during the Treatment Period, as well as the quantity and timing of such medication use during the Treatment Period
- To assess the Daily Sleep Interference Scale (DSIS) score after 12 weeks of treatment

Study Secondary Endpoints

- Proportion of subjects who achieve at least a 30% decrease from baseline in the Week 12 average NPRS pain intensity score
- Proportion of subjects who achieve at least a 50% decrease from baseline in the Week 12 average NPRS pain intensity score
- Proportion of subjects using rescue medication for DPNP, as well as the quantity and timing of such medication use during the Treatment Period
- Change from baseline in the average DSIS score during Week 12

[figure not shown]

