7.1. Adverse Events

All AEs will be classified using MedDRA. In this study, only treatment emergent AEs (TEAEs) i.e. those that occurred or worsened after the first randomized dose will be analyzed. Such AEs will have an onset date on or after the date of first randomized dose or will have presented prior to the first randomized dose and subsequently worsened. Therefore, whenever an analysis of summary of AEs is mentioned, it is intended that this is in reference to treatment-emergent AEs.

Whenever possible, date/time will be used to determine whether an event is treatment emergent. If an event date (start or end) is incomplete, a TEAE will be determined assuming the most conservate way as follows:

- If onset day is missing and the month and year are the same as or after the treatment start date, then that event is considered treatment emergent.
- If both onset month and day are missing and the year is the same as or after the treatment start date, then that event is considered treatment emergent.
- If both onset date and end date are completely missing, an event will be considered as a TEAE.
- If onset date is completely missing and end date is not missing which is after the first randomized dose of study drug, an event will be considered as a TEAE.

The incidence of TEAEs will be summarized by dose level (or cohort) and overall RTA 901 as follows:

- Overall summary of TEAE
- TEAEs by primary SOC and MedDRA preferred term
- TEAEs by MedDRA preferred term
- TEAEs by MedDRA preferred term with incidence of >=2%
- SAEs by primary SOC and MedDRA preferred term
- SAEs by MedDRA preferred term
- Related SAEs by primary SOC and MedDRA preferred term
- TEAEs by maximum severity, primary SOC and MedDRA preferred term
- Related TEAEs by primary SOC and MedDRA preferred term
- TEAEs that led to discontinuation of study treatment by primary SOC and MedDRA preferred term
- TEAEs that led to study drug interruption by primary SOC and MedDRA preferred term
- TEAEs that led to withdrawal from study by primary SOC and MedDRA preferred term

TEAEs that led to death by primary SOC and MedDRA preferred term

For the summary of TEAEs by severity, primary system organ class and/or preferred term, participants will be counted only once within each primary SOC/MedDRA preferred term and will only be counted under the maximum severity.

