For the summary of TEAEs by relationship to study treatment, a subject will be counted only once and in the category of the strongest relationship to study treatment within each SOC/preferred term. The relationship to study treatment will be classified as related or not related.

Also, the AEs during the run-in period will be summarized by primary SOC and MedDRA preferred term.

Listings of all AEs, SAEs, AEs that led to study drug discontinuations, AEs that led to study withdrawals, and AEs that led to study drug interruption will be presented. Listing of death will be provided.

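### SAP 7.1 pools on-drug and off-drug adverse events in one incidence with no stated end, so no AE summary table describes the period after treatment

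*Protocol*

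**What the plan says.** The primary safety objective, in Protocol 2.1.1.2 and repeated in SAP 2.1, is "To assess the safety and tolerability of RTA 901 during and following the Treatment Period". The matching endpoint (Protocol 2.2.1.2) is the frequency, intensity and relationship of AEs and serious AEs, plus change from baseline in examinations, vital signs, ECG, laboratory values and weight.

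SAP 7.1 restricts the AE analysis to "those that occurred or worsened after the first randomized dose will be analyzed". It sets a lower limit, "Such AEs will have an onset date on or after the date of first randomized dose", and no upper limit. The measure is: "The incidence of TEAEs will be summarized by dose level (or cohort) and overall RTA 901". Protocol 8.4.8 shows that this means a count and percentage: "The number and percent of subjects with an AE will be summarized for each treatment group". One AE summary is separated by period, and it is for run-in: "the AEs during the run-in period will be summarized by primary SOC and MedDRA preferred term". AE listings are also planned.

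AEs are collected from consent to the final visit, or to 30 days after the final dose in subjects who terminate early (Protocol 6.1). The SAP's horizon is the Week 16 visit, and the last 4 weeks are off drug (SAP 1 and 2.2). For early stoppers, Protocol 4.6.1 says: "The subject will then complete the procedures associated with the Week 16/end of study (EOS) visit 4 weeks after discontinuation".

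**The concern.** The objective names two periods, and the AE tables describe neither separately. Two consequences follow.

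- **Mixing.** An event that begins three weeks after the last capsule counts the same as one that begins on drug. If the drug raises AE risk only while it is taken, background events in the off-drug weeks pull the risk ratio towards 1. An excess that appears only after stopping would be blended into the 16-week total.
- **Unequal time.** A subject who stops early is observed for weeks on drug plus about 4. A percentage of subjects takes no account of this, so an arm with more early stops has less time in which to record events.

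AE frequency is part of a primary endpoint, and these tables carry the main tolerability comparison of 10 mg and 80 mg with placebo.

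**Working it through.** **Inputs from the documents.** Treatment is 12 weeks and follow-up 4 weeks; the end-of-study visit falls 4 weeks after early discontinuation. The plan's own duration reproduces: 2 + 2 + 12 + 4 = 20 weeks. The plan makes no numerical claim about the AE comparison, so there is no figure to reproduce there.

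**Step 1: time under AE observation.** Observed weeks = weeks on drug + 4; off-drug share = 4 / (weeks on drug + 4).

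| Last dose at | Weeks observed | Share of completer's time | Off-drug share |
|---|---|---|---|
| Week 12 | 16 | 100% | 25% |
| Week 8 | 12 | 75% | 33% |
| Week 4 | 8 | 50% | 50% |
| Week 2 | 6 | 37.5% | 67% |

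Using the 30-day collection rule in place of 28 days changes little: for a Week 4 stop, 30 / 58 = 52% off drug. This step needs no outside assumption.

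**Step 2: effect of mixing (illustration).** Assume a constant background rate b per week, doubled on drug, back to b at the last dose, and no early stops. Risk over 12 weeks is 1 − exp(−12b) on placebo and 1 − exp(−24b) on drug. Over 16 weeks it is 1 − exp(−16b) and 1 − exp(−28b).

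- b = 0.02: on-treatment 21.3% v 38.1%, ratio 1.79, difference 16.8 points. The 16-week table gives 27.4% v 42.9%, ratio 1.57, difference 15.5 points.
- b = 0.005: the ratio is 1.94 on treatment and 1.70 over 16 weeks; the difference is about 5.5 and 5.4 points.

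The ratio shrinks noticeably. The absolute excess barely moves.

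**Step 3: effect of unequal time (illustration).** Assume the same rate, 0.05 per week, in both arms, with stops at Week 4 in 10% on placebo and 25% on 80 mg.

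- 16-week risk: 1 − exp(−0.80) = 55.1%. 8-week risk: 1 − exp(−0.40) = 33.0%.
- Placebo: 0.90 × 55.1 + 0.10 × 33.0 = 52.9%.
- 80 mg: 0.75 × 55.1 + 0.25 × 33.0 = 49.5%.

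That is about 3 points in favour of 80 mg with no true difference. With an assumed 12-week placebo risk of 30% and stopping of 10% v 30% at Week 2 to 4, the ratio under no true difference is 0.88 to 0.91.

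**Step 4: would a period split alone cure this?** No. Under Step 3's assumptions, the on-treatment risks are 1 − exp(−0.60) = 45.1% over 12 weeks and 1 − exp(−0.20) = 18.1% over 4 weeks. Placebo becomes 0.90 × 45.1 + 0.10 × 18.1 = 42.4%, and 80 mg becomes 0.75 × 45.1 + 0.25 × 18.1 = 38.4%. The spurious gap widens to 4.0 points. The split answers the mixing; only person-time answers the unequal follow-up.

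**The case against.** The case for leaving SAP 7.1 alone is substantial.

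- **No promise is broken.** Neither the objective nor the endpoint commits to AE tables by period. A count from first randomized dose through Week 16 covers both periods, and Protocol 6.1.2 also defines treatment emergence without an end. A reader might infer that the SAP contradicts the objective; the documents do not support that.
- **Post-treatment data are not invisible.** A reader might infer that a withdrawal or late effect could not be detected at all. That goes too far. All AEs and serious AEs are listed, Week 16 is a separate visit for laboratory values, vital signs and ECG (SAP 3.1.3), and NPRS and DSIS have weekly windows for Weeks 13 to 16.
- **Early stopping is reported.** Discontinuations with reasons (SAP 5.2), exposure (SAP 5.5) and AEs leading to discontinuation, interruption or withdrawal (SAP 7.1) are all tabulated.
- **The illustrated sizes are assumed and modest.** Three points is about 2 of 64 subjects, against a standard error near 8.8 points, and no safety testing is planned.
- **Any cutoff can misclassify.** The visible text gives no offset time, so ending the on-treatment period at the last dose could move drug-caused events into follow-up.

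All of this stands, and it limits the point to the AE summary tables. It does not remove the gap. A listing is not a comparison between arms, and AE frequency is itself a primary endpoint. The SAP also separates drug exposure from follow-up elsewhere: off-treatment weekly means (SAP 3.1.3), sensitivity analyses without post-discontinuation data (SAP 6.3, 6.4.5) and rescue use per day of exposure (SAP 6.4.4). SAP 3.1.2 even defines days since last dose for events, but SAP 7.1 does not use it.

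**Conclusion.** The point holds as a reporting gap in a descriptive analysis. It is not an error in any stated figure, and it leaves type I error and sample size untouched. What follows from the documents is firm: on-drug and off-drug AEs share one incidence, the off-drug share is 25% for a completer and 50% for a Week 4 stopper, and no AE summary table describes the post-treatment period. SAP 7.1 does not itself name an end of study limit; that end follows from AE collection in Protocol 6.1 and the SAP's Week 16 horizon.

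The consequences are conditional. Dilution requires the AE rate to fall after stopping, and it affects the ratio far more than the difference. A reader might infer that the arm with more discontinuations will look safer by a known amount. The documents do not support that: the effect needs stopping to differ by arm, and the current text gives no dropout rate. Every percentage in Steps 2 to 4 is therefore illustrative.

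**What to change.** In SAP 7.1, keep the combined treatment-emergent tables as planned and add:

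1. A summary of overall AEs, AEs by system organ class and preferred term, and serious AEs, split into on-treatment and post-treatment onset, with the subjects entering each period as the denominators.
2. Events, or first-event incidence, per person-week by arm, so that shorter observation after early stopping is accounted for.
3. A pre-specified, justified cutoff relative to the last dose, including any carry-over allowance. The visible text supports no particular value, so the sponsor must supply and defend one.

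Assigning AEs by onset date is practical because Protocol 6.3 has only total duration and greatest severity of an ongoing AE entered in the eCRF. An event that starts on drug and worsens later would stay in the on-treatment period, and the SAP should say so.

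The inputs exist: AE onset dates, the last-dose date on the end of treatment form (SAP 5.5) and the days-since-last-dose variable (SAP 3.1.2). The cost is a few more tables and possible misclassification of AEs near the cutoff, which keeping the combined table mitigates.
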